Statistical Analysis Plan (SAP)

RAPID-AF: Repetitive Activation Patterns and Focal Impulses Identification and Ablation in Persistent AF using the RHYTHMFINDER-192

Protocol Version: 2.0

This document is a confidential communication. The recipient agrees that no unpublished information contained herein will be published or disclosed without prior written approval. This document may be disclosed to the appropriate ethics committees or to duly authorized representatives of the U.S. Food and Drug Administration or other responsible regulatory authorities, under the condition that they are requested to keep it confidential.

SAP Version: 1.0
SAP Date: 09/06/2017

Revision History

| Revision Number | Revision Date (DD/MM/YYYY) | Reasons for Revision |
|-----------------|-------------------------------|----------------------|
| N/A | | |
| | | |

Table of Contents

| | | |
|----|--|----|
| 1 | Study Design | 6 |
| 2 | Treatment Assignment | 6 |
| 3 | Randomization and Blinding Procedures | 6 |
| 4 | Interval Windows | 7 |
| 5 | Primary and Secondary Endpoint(s) and Associated Hypotheses..... | 7 |
| | 5.1 Study Endpoint(s)..... | 7 |
| | 5.2 Other Endpoints..... | 8 |
| 6 | Levels of Significance..... | 8 |
| 7 | Analysis Sets | 8 |
| 8 | Sample Size Justification..... | 9 |
| 9 | Data Monitoring Committee (DMC)..... | 9 |
| 10 | Analyses to be Conducted..... | 9 |
| | 10.1 General Conventions | 9 |
| | 10.2 Disposition of Study Subjects..... | 10 |
| | 10.3 Demographic and Baseline Characteristics | 10 |
| | 10.4 Endpoint Analyses..... | 11 |
| | 10.5 Plans for Interim Analysis | 13 |
| | 10.6 Handling of Missing Data..... | 13 |
| | 10.7 Sensitivity Analyses | 13 |
| | 10.8 Subgroup Analysis..... | 13 |

| | |
|--|----|
| 10.9 Assessment of Site Homogeneity | 13 |
| Appendix: Tables, Listings and Graphs Shells | 14 |

1 Study Design

The study is a prospective, single arm, non randomized, open label, multicenter study.

The primary purpose of this trial is to assess safety and effectiveness of using the CARTOFINDER™ (CF) maps created by the RHYTHMFINDER (RF) basket catheter () and the CARTOFINDER™ System using the 4D LAT algorithm in treating persistent atrial fibrillation (PsAF).

Subjects who fulfill the inclusion / exclusion criteria and sign the informed consent form will be enrolled in the RAPID-AF study. Approximately 6-10 centers located worldwide will participate the study. The study will enroll approximately 40 to 70 subjects.

An interim analysis will be performed when 20 evaluable subjects are reached, who have the RHYTHMFINDER™ 192 Catheter inserted and CARTOFINDER guided ablation performed. The interim analysis is not proposed in the protocol. Details of the analysis will be described in the section 10.5.

2 Treatment Assignment

All enrolled patients will undergo the CARTOFINDER™ mapping procedure to identify the ablation targets.

The CARTOFINDER™ 4D LAT Algorithm provides automatic analysis of multiple simultaneous ECG signals recorded by a multi-electrode catheter and leads to the generation of a CARTOFINDER™ Map. The CARTOFINDER™ Map may facilitate the identification of ablation targets including Repetitive Activation Patterns (RAPs) or Focal Impulses (FI) or other ablation targets.

Subjects displaying ablation targets on the CARTOFINDER™ (CF) map will undergo CARTOFINDER™ Guided Ablation (CFGa) and subsequently the PVI (WACA) ablation. Subjects not displaying ablation targets on CARTOFINDER™ will be treated per investigator's standard of care and be followed up 7 days after the ablation procedure.

3 Randomization and Blinding Procedures

Not Applicable.

4 Interval Windows

After the index ablation procedure, subjects will enter a 3-Month Blanking Period (Day 0-90) and then a 9-Month Evaluation Period (Day 91-365). During evaluation period, subjects will undergo follow up visits at predefined intervals (at 7 days, 3, 6, and 12 months post the index procedure) to receive study assessments. Subjects will complete the RAPID-AF study after completing the 12-month follow up visit.

| | Screening / Baseline | Ablation Procedure ¹ | Discharge | 7 Days +/- 2 day | 3 Month +/- 1 wks. | 6 Month +/- 2 wks. | 12 Month +/- 4 wks. |
|--|----------------------|---------------------------------|-----------|------------------|--------------------|--------------------|---------------------|
| Informed consent ¹ | X | | | | | | |
| Inclusion & exclusion criteria | X | | | | | | |
| Demographics | X | | | | | | |
| Medical assessment | X [history] | | | X | X | X | X |
| Arrhythmias | X [history] | | X | X | X | X | X |
| ECG (12 lead and CL measurement) | X | | X | | X | X | X |
| NYHA/CHADS ₂ -VASC ₂ score | X | | | | | | |
| Pregnancy Test ² | X | | | | | | |
| Assessment LA Thrombus ³ | | X | | | | | |
| TTE ⁴ | X | | | | | | |
| Ablation assessments | | X | | | | | |
| Arrhythmia Monitoring (Holter) ⁸ | | | | | X | X | X |
| Device Deficiency | | X | | | | | |
| Concomitant Medications ⁵ | X | X | X | X | X | X | X |
| Adverse events ⁶ | X | X | X | X | X | X | X |

1 Informed Consent to be obtained and collected prior to any study specific assessments

2 Pregnancy test must be done on pre-menopausal women only within 1 week prior to procedure.

3 Imaging method as per standard hospital practice (TEE, ICE, ...); within 24 hours prior to procedure

4 Imaging TTE to determine the atrial size (if the subject has undergone an imaging procedure within the last 6-months where the atrial size was assessed, the pre-procedure imaging assessment is not required). If LA diameter is ≥ 47 mm, LA volume to be measured.

5 Concomitant medications: only cardiac related (AAD drugs, anticoagulation regimen, etc.).

6 AEs will be collected once consent has been signed

7 End of study (CRF) page to be completed for ALL enrolled subjects

8 Holter: Dispensation of Holter device at Month 3 visit, 24-hour Holter monitoring at 3 month and ≥ 72 -hour Holter monitoring at 6 and 12 months follow-up.

5 Primary and Secondary Endpoint(s) and Associated Hypotheses

No formal statistical hypothesis was formulated.

5.1 Study Endpoint(s)

Effectiveness

- Acute success defined as: Rate of conversion of Atrial Fibrillation to Normal Sinus Rhythm or Atrial Tachycardia, after CFGA and PVI (without cardioversion)
- Procedural success defined as: Conversion of Atrial Fibrillation to Normal Sinus Rhythm or Atrial Tachycardia after overall ablation procedure, with or without the need for cardioversion
- Rate of conversion of Atrial Fibrillation to Normal Sinus Rhythm or Atrial Tachycardia, after CFGA only (before PVI and without cardioversion)
- Freedom from documented symptomatic AF/AT/AFL recurrence (episodes ≥ 30 seconds on an arrhythmia monitoring device) post the 3-month blanking period through the 12-month follow up.

- Incidence of PVI (confirmed entrance block) after adenosine/isoproterenol challenge
- Change of intra-cycle length from pre-CFGA to post-CFGA and post-PVI

Safety

- Incidence of early-onset Primary Adverse Events
- Incidence of study device and procedural related SAEs during follow-up period (12M)
- Incidence of all SAEs during follow-up period (12M)
- Incidence of study device and procedure related adverse events

5.2 Other Endpoints

- Investigational Device Performance
 - Number of identified CF ablation targets
 - Max number of active RF 192 electrodes during initial mapping procedure
- AAD use post the 3-month blanking period
- Incidence of repeat ablation procedures for AF post the 3-month blanking period
- Procedural data
 - All target sites for RF lesion application
 - Location of ablation targets
 - Number of RF applications per target
 - Total RF duration per application
 - RF ablation parameters (including but not limited to: power, contact force, impedance, flow rate, temperature)
 - Total fluoroscopy time and dose
 - Total procedure, mapping and ablation time

6 Levels of Significance

No formal statistical hypothesis and inferential statistics will be formulated and performed. Two-sided 95% confidence intervals will be constructed for the effectiveness and safety endpoints.

7 Analysis Sets

The following analyses populations will be used to complete the analyses of the data:

- **Safety Subject Population (SP)**: The safety subject population will include all enrolled subjects who have the RHYTHMFINDER™ 192 Catheter inserted, regardless if CARTOFINDER guided ablation was performed.
- **Evaluable Subject Population (EP)**: The evaluable subject population will include all enrolled subjects who have the RHYTHMFINDER™ 192 Catheter inserted and where CARTOFINDER guided ablation was performed.

- **Effectiveness Subject Population (Efp):** The effectiveness subject population will include all Evaluable Subjects who meet the study eligibility criteria. Efp was not included in the protocol but added in the SAP.

8 Sample Size Justification

This is a feasibility study of safety and effectiveness in which the sample size of the clinical investigation is intended to provide preliminary estimates of these two aspects. Enrollment in the clinical investigation will be approximately 40-70 evaluable subjects.

9 Data Monitoring Committee (DMC)

No Data Monitoring Committee will be constituted for the study.

10 Analyses to be Conducted

10.1 General Conventions

- Descriptive statistics for categorical variables will include frequency and percentage. If not otherwise specified, the percentages will be calculated as the number of subjects or events divided by the total number of subjects or events with non-missing data in the specified analysis population. In the calculation of the percentage of subjects having a specific adverse event, the subject will only be counted once even if the subject had the same adverse event multiple times.
- The 95% binomial exact confidence intervals for proportions will be exact if not otherwise specified.
- Descriptive statistics for continuous variables will include at a minimum, number of subjects, mean, standard deviation, median, minimum and maximum.
- The analysis of data will require that the number of days since the initial ablation be calculated. The Study Day will be calculated as: (date of the occurrence of event – initial ablation date).

Note: The day of initial ablation is considered Study Day 0. The “event” in the above definition includes: recurrence of atrial tachyarrhythmias, onset of AEs, etc.

- Data displays will include three types - summary tables, data listings and figures. Unless stated otherwise, data listings will be produced for all critical data points.
- SAS Studio will be used for the analysis.

10.2 Disposition of Study Subjects

The following subject dispositions are defined:

- **Enrolled Subjects**: Subjects who have signed and dated the Informed Consent Form.
- **Excluded Subjects**: Enrolled subjects who have signed an ICF but are found not meeting eligibility criteria prior to insertion of the RHYTHMFINDER™ 192 Catheter.
- **Mapping Failure**: Enrolled subjects who have the RHYTHMFINDER™ 192 Catheter inserted but inability to record baseline CF mapping signals is observed, will be followed up for 7 days. If an SAE is reported for a mapping failure subject, they will be followed until event resolution or stabilized. The investigator will document mapping failures in the electronic CRF, including reasons for failure.
- **Discontinued Subjects**: Enrolled subjects who have the RHYTHMFINDER™ 192 Catheter inserted but do not undergo CF guided ablation. If subject's arrhythmia is determined at the time of EP study to be a non-study arrhythmia (required for subject enrollment per study inclusion criteria), the subject will be categorized as discontinued subject. Discontinued subjects will remain in follow-up for 7 days. If an SAE is reported for a discontinued subject, they will be followed until event resolution or stabilized.
- **Lost to Follow-up Subjects**: Subjects who are enrolled and have the RHYTHMFINDER™ 192 Catheter inserted, but contact is lost after most recent follow-up visit (despite 3 documented attempts to contact the subject).
- **Withdrawn / Early Termination Subjects**: Subjects who have RHYTHMFINDER™ 192 Catheter inserted but withdraw consent for study participation or are withdrawn by the investigator or are terminated from the study prior to completion of all follow-up visits
- **Completed Subjects**: enrolled subjects who complete the last scheduled follow-up visit per study protocol.

Subject's disposition will be summarized for all enrolled subjects.

10.3 Demographic and Baseline Characteristics

- Demographics

Descriptive statistics for the continuous variable (age) and frequency counts and percentages for the categorical demographics variable (gender) will be summarized for all enrolled subjects.

- **Baseline Characteristics**

Baseline characteristics, including Medical History Conditions, New York Heart Association (NYHA) Class, CHADS² score / CHA²DS²-VASc score, Persistent AF History, Failed AAD Medication History at screening, Preganancy Test, TTE Exam, Visualization of LA Thrombus assessment, and ECG, will be summarized overall for all enrolled subjects. Descriptive statistics for continuous and categorical variables will be presented.

10.4 Endpoint Analyses

Descriptive statistics and two-sided 95% confidence intervals will be presented for the effectiveness and safety endpoints. No formal statistical hypothesis and inferential statistics will be formulated and performed. Analyses of all endpoints will be performed in the proposed analysis populations excluding the subjects with missing outcomes.

- **Safety**

The incidence of early-onset Primary Adverse Events is the percentage of patients with at least one primary adverse event with onset on Day 0 through Day 7 except for pulmonary vein (PV) stenosis and atrio-esophageal fistula that could occur greater than one week (7 days) post-procedure . The number of primary adverse events and the number of subjects experiencing primary adverse events will be reported.

Incidence of (S)AEs during the 12 month follow-up will be reported as the number of (S)AEs and the number of subjects experiencing (S)AEs. The number and percentage of subjects with (S)AEs will be summarized overall and by AE type, seriousness, severity, relationship to device and procedure, anticipated or not and outcome. Listing of (S)AEs will also be provided.

The SP will be used as the analysis population.

- **Effectiveness**

Effectiveness outcomes includes

1. **Acute Success**: Rate of conversion of Atrial Fibrillation to Normal Sinus Rhythm or Atrial Tachycardia, after CFGA and PVI (without cardioversion)

2. **Procedural Success**: Conversion of Atrial Fibrillation to Normal Sinus Rhythm or Atrial Tachycardia after overall ablation procedure, with or without the need for cardioversion
3. **Acute Success Post-CFGA**: Rate of conversion of Atrial Fibrillation to Normal Sinus Rhythm or Atrial Tachycardia, after CFGA only (before PVI and without cardioversion)
4. Incidence of confirmed entrance block post-PVI after adenosine/isoproterenol challenge
5. Freedom from documented symptomatic AF/AT/AFL recurrence (episodes \geq 30 seconds on an arrhythmia monitoring device) post the 3-month blanking period through the 12-month follow up.
6. Change of intra-cycle length from pre-CFGA to post-CFGA and post-PVI

The number and percentages of subjects with effectiveness endpoints (#1- #5) and the corresponding two-sided 95% binomial confidence intervals will be presented.

The descriptive statistics for pre-CFGA, post-CFGA and post-PVI cycle length will be presented. The changes from pre-CFGA cycle length at each ablation procedure steps (post-CFGA and post-PVI) will also be summarized

The EP and EffP will be used as the analysis population for all effectiveness endpoints.

- Other Study Assessments
 - AAD use post the 3-month blanking period
 - Incidence of repeat ablation procedures for AF post the 3-month blanking period

The descriptive statistics for the above endpoints will be summarized in EP.

- Investigational Device Performance

Investigational device performance will be reported as the number of ablation targets identified and the maximum % of active electrodes. Investigational device performance will also be reported by means of survey questions. Listings of survey answers/scoring will also be provided.

- Procedural Data

Procedural data including but not limited to procedure duration, mapping duration, fluoroscopy time, RF application time, number of RF application, power, contact force, impedance, temperature, and location of ablation targets will be summarized with descriptive statistics and listed.

These analyses will be conducted in the EP.

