10.6 Handling of Missing Data

Missing data will be queried for reasons and will not be imputed.

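### The 12-month freedom-from-recurrence rate is a crude percentage with no censoring and no definition of "missing" for subjects who leave early; on the most natural reading it is biased down on average

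*SAP*

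**What the plan says.** Effectiveness outcome 5 in SAP 10.4 is "Freedom from documented symptomatic AF/AT/AFL recurrence", counted after the 3-month blanking period and through the 12-month follow-up. SAP 4 sets the evaluation period at Day 91 to Day 365.

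- **Estimator (SAP 10.4):** "The number and percentages of subjects with effectiveness endpoints (#1- #5) and the corresponding two-sided 95% binomial confidence intervals will be presented". SAP 10.1 makes the intervals exact.
- **Exclusion (SAP 10.4, and the same rule in protocol 15.3):** "Analyses of all endpoints will be performed in the proposed analysis populations excluding the subjects with missing outcomes".
- **Denominator (SAP 10.1):** "the percentages will be calculated as the number of subjects or events divided by the total number of subjects or events with non-missing data".
- **Imputation (SAP 10.6, and protocol 15.4):** "Missing data will be queried for reasons and will not be imputed".
- **Early leavers (SAP 10.2):** withdrawn subjects, including those "terminated from the study prior to completion of all follow-up visits", and lost subjects are disposition categories. No endpoint status is attached to either.
- **Sensitivity (SAP 10.7):** the effectiveness endpoints are repeated in the Effectiveness Subject Population. That changes the population by eligibility, not the handling of withdrawals.

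No section gives a time-to-event method, a censoring rule or a definition of a missing 12-month outcome.

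**The concern.** Failure and success need different amounts of follow-up. One documented recurrence at month 5 settles a subject's outcome, whatever happens later. A subject who is recurrence-free on the 6-month Holter and withdraws at month 7 has no complete outcome through month 12. If the first stays in and the second is removed, being excluded depends on the outcome, and the removed subject's recurrence-free follow-up does not enter the estimate.

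SAP 8 says the sample size is meant to give preliminary estimates of safety and effectiveness, and outcome 5 is the only 12-month rhythm endpoint among the effectiveness outcomes. A bias from the missing-data rule would not show in the binomial interval. Leaving the term undefined in an open-label, single-arm study also allows the classification to be settled after the outcomes are known.

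**Working it through.** The plan gives no expected freedom rate and no withdrawal rate, so there is no planned figure to reproduce.

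**Assumptions for the size.** True freedom S = 50%, the middle of the 40% to 60% range that protocol 2.1 quotes for one procedure (background, not a design assumption here). Constant recurrence hazard over Day 91-365, scaled to [0, 1]. Withdrawal independent of recurrence, in a proportion d.

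**Three readings of "missing"**

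- A: keep withdrawn subjects who had recurred, drop withdrawn subjects who were free.
- B: drop every withdrawn subject.
- C: count a withdrawn subject with no documented recurrence as free.

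B would discard recurrences that were actually observed. C credits months that nobody observed. A fits the exclusion, denominator and no-imputation rules together best.

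**Reading A, withdrawal at a constant rate over Day 91-365.** Let λ = -ln S = 0.693 and μ = -ln(1-d). The expected rate is

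S(1-d) / { S(1-d) + [λ/(λ+μ)] × [1 - S(1-d)] }

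- d = 10%: 0.45 / (0.45 + 0.868 × 0.55) = 48.5%
- d = 20%: 0.40 / (0.40 + 0.756 × 0.60) = 46.8%
- d = 30%: 0.35 / (0.35 + 0.660 × 0.65) = 44.9%

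**Reading A, other timing.** Let m be the mean probability of still being free when withdrawal occurs. The expected rate is S(1-d) / [(1-d) + d(1-m)].

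- Spread evenly over Day 0-365: m = [90 + 275 × (0.5/0.693)]/365 = 0.790. At d = 10%, 0.45/(0.90 + 0.021) = 48.9%. At 20%, 0.40/(0.80 + 0.042) = 47.5%. At 30%, 0.35/(0.70 + 0.063) = 45.9%.
- All near month 11 (89% of the interval): m = 0.5^0.89 = 0.540. The rates are 47.6%, 44.8% and 41.8%.

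| Withdrawal | A, Day 0-365 | A, Day 91-365 | A, near month 11 | B | C, Day 0-365 |
|---|---|---|---|---|---|
| 10% | 48.9% | 48.5% | 47.6% | 50.0% | 52.9% |
| 20% | 47.5% | 46.8% | 44.8% | 50.0% | 55.8% |
| 30% | 45.9% | 44.9% | 41.8% | 50.0% | 58.7% |

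Column C is S(1-d) + dm; for example 0.45 + 0.1 × 0.790 = 52.9%.

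**Crude rate against Kaplan-Meier.** Take 50 evaluable subjects: 15 recur by month 7, 8 withdraw free at month 7, 7 more recur, 20 finish free.

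- Crude (A): 20/(20 + 22) = 20/42 = 47.6%, exact 95% CI 32.0% to 63.6%.
- Kaplan-Meier: 35/50 × 20/27 = 51.9%.

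To isolate the asymmetry, suppose 3 of the 15 early recurrers also withdraw, roughly the same share as 8 of 35. Reading A still gives 20/42. Reading B gives 20/39 = 51.3%, close to Kaplan-Meier.

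**Size against the interval.** Take 70 subjects and 7 withdrawals, 2 of them after recurrence, with 32 of 63 completers free:

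- A: 32/65 = 49.2% (36.6% to 61.9%)
- B: 32/63 = 50.8% (37.9% to 63.6%)
- C: 37/70 = 52.9% (40.6% to 64.9%)

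**The case against.** The strongest reply is that the plan never states reading A. Excluding missing outcomes without defining them is an ambiguity, and B and C give no bias and an upward bias. This stands: the direction is conditional on the reading. It does not rescue the plan, because B throws away observed recurrences, C is biased up, and the text does not choose between them. The separate table shells that the SAP appendix cites were not available and might settle it.

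A reader might infer that every withdrawal pushes the rate down. That is false even under A. Starting from 35/70 = 50.0%, a withdrawal after recurrence changes nothing. A free subject who would have stayed free gives 34/69 = 49.3%, and one who would have recurred gives 35/69 = 50.7%. Withdrawals during blanking have no expected effect.

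Informative withdrawal can reverse the sign. With 63 completers at 50%, 2 recurred leavers and 5 free leavers, A gives 31.5/65 = 48.5%. Full follow-up would give (31.5 + 1.5)/70 = 47.1% if 30% of the 5 stayed free, and (31.5 + 3.5)/70 = 50.0% if 70% did.

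A reader might also infer that a procedure stopped before PVI is complete drops out of procedural success (outcome 2). The documents do not support that. Outcome 2 is judged after the whole ablation procedure, and protocol 7.1 collects rhythm before and after ablation, so the value need not be missing. Outcomes 1 and 4 do depend on PVI, and the evaluable population requires only catheter insertion and CARTOFINDER-guided ablation, so the gap is possible there. As a hypothetical size, 30 conversions with 2 of 50 procedures stopped give 30/48 = 62.5% or 30/50 = 60.0%.

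Finally, the study has no hypothesis or decision threshold, and the differences are small against the interval. Both are true, and they limit the weight of the point.

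**Conclusion.** The point holds as a gap in definition combined with a weaker estimator than the data allow. On the most natural reading, and if withdrawal is independent of prognosis, the crude rate is biased down on average. At an assumed true freedom of 50%, the shortfall is 1.1 to 5.1 points for 10% to 30% withdrawal spread over follow-up, and 2.4 to 8.2 points if withdrawals fall near month 11. The withdrawal rate, its timing, the constant hazard and the true rate are all assumptions, since the documents give none of them for this trial. A downward bias in the final result is not established: another reading or informative withdrawal could remove or reverse it. The change is worth making but is not critical to a descriptive feasibility study.

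**What to change.** In SAP 10.4, estimate outcome 5 by Kaplan-Meier:

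- Start at the end of blanking (Day 91). The event is the first qualifying recurrence, and other subjects are censored at their last rhythm assessment.
- Treat subjects who complete the 12-month visit within its +/-4 week window as followed to 12 months. Otherwise a recurrence-free completer seen before Day 365 would be censored early. State also how a recurrence first recorded at a visit after Day 365 counts.
- Report the 12-month estimate with a 95% CI.
- Keep the crude percentage as a supporting line, and state which withdrawn and lost subjects it excludes.

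For outcomes 1 and 4, at most add that an evaluable subject whose PVI was not completed stays in the denominator as not achieving the endpoint. Outcome 2 should use the rhythm recorded at the end of the procedure.

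The cost is SAP wording and one extra table or figure. No new data are needed, because SAP 10.1 already computes the Study Day of recurrence, and no value is imputed. Three limits remain. Scheduled Holters fall only at months 3, 6 and 12, so Holter-detected events will cluster at visits. Kaplan-Meier is approximately unbiased only if withdrawal is independent of prognosis. Rates for outcomes 1 and 4 may come out slightly lower.

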Study Devices	RHYTHMFINDER basket catheter (Investigational) CARTOFINDER™ workstation (CE-mark) CARTO® 3 with CARTOFINDER™ module (CE-mark)
Scope and study centers	Geographic involvement may include centers worldwide, mainly Europe and Canada. Approximately 6 to 10 centers worldwide will participate
Study Population	All subjects with persistent AF who are scheduled to undergo a clinically-indicated ablation procedure for management of their persistent AF will be the target population for screening.
Study Design	The study will enroll approximately 40-70 subjects. Subjects will undergo CARTOFINDER™ guided ablation (CFGA) followed by PVI. Subjects will have follow-up visits at 7 days, 3, 6 and 12 months post-procedure. Subjects where no CF ablation target is identified on the baseline CARTOFINDER™ map using the RHYTHMFINDER™ 192 Catheter, will exit the study after 7 day follow up.
Study Duration	Approximately 20 months (8 months recruitment, 12 months follow-up)

Study Endpoints
	
Effectiveness
 
 • Acute success defined as: Rate of conversion of Atrial Fibrillation to Normal Sinus Rhythm or Atrial Tachycardia, after CFGA and PVI (without cardioversion) • Procedural success defined as: Conversion of Atrial Fibrillation to Normal Sinus Rhythm or Atrial Tachycardia after CFGA and PVI, with or without the need for cardioversion • Rate of conversion of Atrial Fibrillation to Normal Sinus Rhythm or Atrial Tachycardia, after CFGA only (before PVI and without cardioversion) • Freedom from documented symptomatic AF/AT/AFL recurrence (episodes \geq 30 seconds on an arrhythmia monitoring device) post the 3-month blanking period through the 12-month follow up. • Incidence of PVI (entrance block) after adenosine/isoproterenol challenge • Change of intra-cycle length from pre-CFGA to post-CFGA and post-PVI 
Safety
 
 • Incidence of early-onset primary adverse events within 7 days of the ablation procedure. • Incidence of study device and procedural related SAEs during follow-up period (12M) • Incidence of all SAEs during follow-up period (12M) • Incidence of study device and procedure related adverse events
------------------------	---

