6.4 Analysis of the CARTOFINDER™ Baseline Map

After completion of the CARTOFINDER™ baseline mapping procedure, the CARTOFINDER™ maps will be

processed and analyzed for the presences of ablation targets including FI/RAPs by the treating/ablating investigator who has been trained by Biosense Webster personnel knowledgeable in analyzing CF maps and the operation of the CARTOFINDER™ system.

Ablation Targets (FI/RAP) identification:

- Identify areas with ablation targets including focal impulse (FI) or repetitive activation patterns (RAPs)
 - If an ablation target is identified, the subject will receive CFGA followed by PVI
 - If no CF ablation target is identified, the subject will be treated per standard of care and exits the study after 7 day follow up.

No RF ablation should occur prior to analysis of the CARTOFINDER™ Maps.

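### The last scheduled safety contact for subjects who exit early may fall on Day 5 or 6, while the early-onset Primary Adverse Event rate runs through Day 7

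*SAP*

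**What the plan says.** **Endpoint.** SAP 10.4 counts subjects with "at least one primary adverse event with onset on Day 0 through Day 7". Pulmonary vein stenosis and atrio-esophageal fistula are excepted and also count after Day 7. SAP 10.1 fixes the day numbering: "The day of initial ablation is considered Study Day 0".

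**Population.** For safety, "The SP will be used as the analysis population". SAP 7 defines that population as "all enrolled subjects who have the RHYTHMFINDER™ 192 Catheter inserted, regardless if CARTOFINDER guided ablation was performed".

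**Contact window.** Protocol Table 7.4 and SAP 4 both schedule the 7-day contact with a tolerance of 2 days either side. Protocol 7.3 allows it to be a telephone call.

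**Who leaves at that contact.**
- A subject without an ablation target "exits the study after 7 day follow up" (Protocol 6.4; the Synopsis says the same).
- For mapping failures, SAP 10.2 says that where "inability to record baseline CF mapping signals is observed, will be followed up for 7 days".
- For the third group, "Discontinued subjects will remain in follow-up for 7 days" (SAP 10.2).

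For the last two groups, follow-up is extended only if a serious adverse event is reported. The Synopsis procedural flow and Protocol 5 likewise describe follow-up of no-target subjects as lasting until 7 days after the procedure.

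**Missing data.** SAP 10.4 excludes subjects with missing outcomes, and SAP 10.6 rules out imputation. Neither says whether a last contact before Day 7 makes the outcome missing.

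**The concern.** A site can follow the schedule exactly, telephone an exit subject on Day 5, complete the last scheduled visit and close the case. Nobody is then scheduled to ask about Days 6 and 7. A guided-ablation subject contacted on the same day is asked about adverse events again at 3 months, so a Day 6 or Day 7 onset can still be picked up. Active ascertainment within one denominator therefore depends on whether guided ablation was done.

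The subjects with the shorter active window had the investigational basket inserted. They are in the Safety Population because its definition does not require guided ablation. An event missed in them lowers the reported rate, and nothing in the plan pushes the other way. Onset after Day 5 is not excluded by the event definitions: tamponade or perforation, for example, is defined in Protocol Table 14.4 with a horizon of 30 days from the procedure.

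The two sets of text also disagree. One gives exit subjects 7 days of follow-up, and the other lets the contact that closes follow-up occur on Day 5.

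**Working it through.** The documents give no expected event rate, exit share or onset distribution, so there is no stated figure to reproduce. The check is calendar arithmetic followed by a range under stated assumptions.

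**Step 1: days without scheduled questioning.** Inputs are Day 0 = ablation day (SAP 10.1), the contact window 7 ± 2 = Day 5 to Day 9 (Protocol Table 7.4, SAP 4), and the endpoint window Day 0 to Day 7 = 8 days (SAP 10.4). I treat the contact day as fully covered, and for an exit subject with no ablation I take the procedure day as Day 0. Days not covered = max(0, 7 − contact day).

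| Contact day | Days not covered | Share of 8 days |
|---|---|---|
| 5 | 2 | 25% |
| 6 | 1 | 12.5% |
| 7, 8 or 9 | 0 | 0% |

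If contacts spread evenly over the five days (assumption), 2/5 = 40% fall before Day 7. The mean loss is (2 + 1 + 0 + 0 + 0)/5 = 0.6 days, or 0.6/8 = 7.5% of the window.

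**Step 2: effect on the rate.** Let s be the share of the Safety Population that exits at this contact, and m the share of Day 0-7 onsets not covered in those subjects. If exit subjects have the same event risk as the rest and passive reporting finds nothing (the worst case), the relative under-count is s × m.

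- s = 20% (assumption), onsets even over 8 days, contacts spread evenly: 0.20 × 0.075 = 1.5%.
- s = 20%, onsets even, every contact on Day 5: 0.20 × 0.25 = 5%.
- Every contact on Day 5, s from 5% to 40%, onsets even: 0.05 × 0.25 = 1.25% to 0.40 × 0.25 = 10%.
- Every contact on Day 5, s from 5% to 40%, only 10% of onsets on Days 6-7: 0.05 × 0.10 = 0.5% to 0.40 × 0.10 = 4%.

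**Step 3: compare with the precision.** With 40 evaluable subjects and s = 20%, the Safety Population is 40/0.8 = 50, of whom 10 exit. Two subjects with events give 2/50 = 4.0%, exact 95% interval 0.5% to 13.7%. On a 4% rate, an under-count of 1.5% to 5% is 0.06 to 0.2 percentage points. If one event were in fact missed, finding it would give 3/50 = 6.0% (1.2% to 16.6%). That is the size of a single miss, not its expected effect.

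**Step 4: test an obvious remedy.** One could drop event-free subjects whose last contact was before Day 7. In the same illustration, 40% of 10 exits is 4 subjects, and 2/50 = 4.0% becomes 2/46 = 4.3%, a relative rise of 50/46 − 1 = 8.7%. Subjects with events stay while event-free ones leave, so this upward shift exceeds the 1.5% to 5% it is meant to cure.

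**Step 5: test the window change.** With the contact at Day 7 to Day 9, the days not covered are 0 for every exiting subject. The two excepted events remain open, because they count after Day 7 and exit subjects have no scheduled contact then.

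**The case against.** A visit window is not a follow-up period, and the documents do give exit subjects 7 days of follow-up. Protocol 14.2 has adverse events recorded whenever the investigator becomes aware of them and encourages spontaneous reports. Protocol 14.3 obliges the investigator to arrange follow-up suited to learning of serious events. A reader might infer that Days 6 and 7 are wholly unobserved, but the documents do not support that: what is lost is scheduled questioning, not all reporting. What stands is that no text requires the contact to fall on or after Day 7, that completion is tied to the last scheduled visit (SAP 10.2), and that the extension for a serious event depends on its having been reported.

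A reader might also infer that a subject contacted on Day 5 will certainly be counted as event-free. SAP 10.4 excludes missing outcomes and is silent on observation that ends early. Counting such a subject as event-free is the likely reading, because the 7-day contact was completed, but it remains an inference.

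It would be too strong to call this the main safety endpoint. It is the first of four listed without rank, in a descriptive feasibility study with no hypothesis. Nor do all subjects called discontinued matter here: Protocol 6.3.1 uses that word for subjects not in AF before catheter insertion, and they are outside the Safety Population.

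Finally, the even-onset assumption may overstate the loss, since many of the listed events are procedural complications and may cluster early. That is fair, and it is why the range includes a case with only 10% of onsets on Days 6-7.

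**Conclusion.** The point holds as a narrow gap in active ascertainment. For Safety Population subjects who exit without guided ablation, up to 2 of the 8 endpoint days may have no scheduled safety question, and the early allowance conflicts with the plan's own 7-day follow-up wording. The direction is downward only. With 20% exits, even onset and no passive detection, the relative under-count is about 1.5% (contacts spread evenly) to 5% (all on Day 5), which is small beside an interval such as 0.5% to 13.7%. The exit share, onset timing and equal risk are all assumptions.

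A reader might conclude that the safety rate is materially biased. These figures do not support that. The case for acting is that the gap is one-directional, hard to recover once subjects have left, and cheap to close.

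**What to change.** 1. In Protocol Table 7.4 and SAP 4, set the 7-day contact at Day 7 to Day 9 (+2/−0) for subjects who exit at that contact. This also reconciles the window with the 7-day follow-up wording in the Synopsis, Protocol 5, Protocol 11 and SAP 10.2.
2. In SAP 10.4, keep all Safety Population subjects in the Primary Adverse Event rate, and say that a last contact before Day 7 does not by itself make the outcome missing. Do not exclude event-free subjects contacted early.
3. Report beside the rate the number of exit subjects whose last safety contact was before Day 7.
4. State in SAP 10.4 that pulmonary vein stenosis and atrio-esophageal fistula with onset after Day 7 are not actively ascertained in exit subjects. The window change does not cover these.

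The cost is one window entry in each schedule table, a few SAP sentences and one reported count. Scheduling becomes slightly less flexible for a contact that may be a telephone call.
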